16.0 Statistical Considerations and Methodology

16.1 Sample Size Determination

The primary objective of this study is to determine whether apixaban 2.5 mg twice daily has less bleeding (major bleeding plus clinically relevant nonmajor bleeding) compared to apixaban 5 mg twice daily for secondary VTE prevention in patients with active cancer, previously confirmed deep-vein thrombosis (DVT) or pulmonary embolism (PE) for which they have completed at least 6 months (but no more than 12 months) of anticoagulant therapy. Important assumptions include both clinical and trial observation that bleeding rates in cancer patients with VTE are higher than non-cancer patients. As such, a recent meta-analysis of cancer patients treated with direct factor inhibitors showed that rates of major bleeding were 3.2% and clinically relevant non-major bleeding 14.5% (19). This would equate to rates of 17.7% for these combined outcomes.

The trial is designed as a two-arm, double-blind, randomized study. Patients will be randomized at a 1:1 ratio to receive either 5 mg or 2.5 mg of apixaban twice daily. Assuming the combined bleeding event rate is 9% in the 2.5 mg arm, and 18% in the 5 mg arm, a sample size of 352 (176 per arm) will give us approximately 70% power to detect a difference between the two arms (using a two-sample comparison of proportions with a two-sided alternative at a 5% significance level). The sample size is inflated by 5% to a total of 370 (185) to account for ineligibility and cancellation. We anticipate accruing 15 patients per month to this trial. Based on this accrual rate, we anticipate the trial will complete accrual in 24 months. With the last patient accrued followed for 12 months, the primary analysis will be conducted approximately 36 months after the trial opening. The sample was calculated using EAST 6.3 (Cytel Inc.).

16.2 Primary Hypothesis:

We hypothesize that apixaban 2.5 mg twice daily is associated with a significantly lower combined rate of major bleed plus clinically relevant nonmajor bleed compared to apixaban 5 mg twice daily for the secondary prevention of VTE in patients with active cancer and confirmed deep-vein thrombosis (DVT) or pulmonary embolism (PE) who have completed at least 6 months (but no more than 12 months) of anticoagulant therapy.

16.21 Primary Safety Analysis:

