All patients who received at least one dose of either apixaban 2.5 mg or apixaban 5 mg will be included in the primary analysis. Patients will be analyzed according to the drug they received because this is a safety analysis rather than an efficacy analysis. The analysis of major bleeding plus clinically relevant nonmajor bleeding events will primarily focus on those events which occurred during treatment or within 7 days of treatment discontinuation. Major bleeding events observed later will be described separately.

It should be noted that this study is powered for our primary analysis, in which the proportion of patients experiencing at least one bleeding event within 12 months of beginning treatment will be compared across the two study arms using a two-sample comparison of proportions with a one-sided alternative at a significance level of 5% (i.e. a “Z” test).

Though **not part of the primary analysis**, a number of additional analyses of the primary endpoint will also be performed to further explore the data. These should be viewed as additional secondary analyses. In particular, frequency of major bleeding and clinically relevant non-major bleeding will be tabulated by treatment arm. Incidence of major bleeding and clinically relevant non-major bleeding will be estimated using the cumulative incidence function with death without major bleeding or clinically relevant non-major bleeding and with adverse events that results in termination of treatment (including vascular events) as competing risks. The time to event is defined as the time from randomization to the first occurrence of a major bleeding, a clinically relevant non-major bleeding, death without major bleeding or clinically relevant non-major bleeding, or an adverse events that results in termination of treatment (including vascular events). Patients who were lost to follow-up, who withdrew informed consent before the end of the predefined study duration will be censored at the last day the patient had a complete assessment for study outcomes within the intended

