study period. The incidence curves of major bleeding and clinically relevant non-major bleeding will be plotted. The incidence of major bleeding and clinically relevant non-major bleeding will be summarized as a combined endpoint and separate endpoints by treatment arm. The difference in the incidences of the combined endpoint at 6 months and at 12 months between treatment arms will be estimated and tested using a normal approximation of the binomial distribution. All tests will be conducted at the one-sided 0.05 significance level.

The incidences of death due to cancer or other causes (without major bleeding or clinically relevant non-major bleeding) and adverse events that result in termination of treatment will be estimated and compared using the same approach.

A sensitivity analysis for these endpoints will be conducted using a stratified (by stratification factors listed in Section 5.0) Cox model adjusting for baseline covariates including location of DVT, renal clearance, age, sex, mobility at randomization, pulmonary disease, and cardiac disease.

16.22 Secondary Safety Analysis:

A secondary safety analysis of the primary safety endpoint will be performed on an intent-to-treat basis using the same approach described in Section 16.21. In addition, we will compare proportion of patients who experience at least one bleeding event (i.e. the primary endpoint) within 6 months of beginning treatment across the two study arms. As with the primary analysis, this will be done using a two-sample comparison of proportions with a one-sided alternative at a significance level of 5%.

16.23 Secondary Efficacy Analysis:

For the secondary efficacy analysis, the time to the first event of the composite DVT/PE outcome will be analyzed using the same method described in Section 16.21. For this outcome, death without DVT/PE and adverse events leading to termination of treatment will be treated as the competing risks.

16.3 Handling of Missing Data:

Monitoring and auditing procedures should be followed, in order to comply with Good Clinical Practice (GCP) guidelines. Each center will be audited at regular intervals to ensure compliance with the protocol, GCP and legal aspects. This will include on-site checking of the CRF for completeness and clarity, cross-checking with source documents, and clarification of administrative matters.

16.4 Interim Analysis and Study Monitoring:

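### The trial is sized for a two-sided 5% test, but its primary analysis is a one-sided 5% test, so the stated 70% power and the planned error rate belong to different tests

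*Combined protocol and SAP*

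**What the plan says.** Section 16.1 (Sample Size Determination) gives the design inputs: "Assuming the combined bleeding event rate is 9% in the 2.5 mg arm, and 18% in the 5 mg arm", with 1:1 allocation. It concludes that "a sample size of 352 (176 per arm) will give us approximately 70% power to detect a difference between the two arms", and names the test as "using a two-sample comparison of proportions with a two-sided alternative at a 5% significance level". The total is then raised by 5% to 370 (185 per arm).

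Section 16.21 (Primary Safety Analysis) ties that calculation to the primary test: "It should be noted that this study is powered for our primary analysis". It defines that analysis, on the 12-month proportion with at least one bleed, as a "two-sample comparison of proportions with a one-sided alternative at a significance level of 5" percent (a Z test).

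One-sided 5% appears twice more. Section 16.21 closes its additional analyses of the primary endpoint with "All tests will be conducted at the one-sided 0.05 significance level". Section 16.22 says of the 6-month comparison: "As with the primary analysis, this will be done using a two-sample comparison of proportions with a one-sided alternative at a significance level of 5" percent.

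The hypothesis in Section 16.2 is directional: less bleeding on 2.5 mg. One-sided 2.5% appears nowhere, and no passage explains why sizing and analysis differ.

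**The concern.** The trial has one primary test, and success is a claim in one direction. For such a claim, the relevant error is the chance of concluding that 2.5 mg bleeds less when the two doses bleed equally. A two-sided 5% test allows 2.5% in that direction; a one-sided 5% test allows 5% and is equivalent to a two-sided 10% test. Someone who takes the design level from Section 16.1 would expect half the error that the planned analysis permits.

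The stated power has the same problem. Section 16.21 says the study is powered for its analysis, yet the only power figure in the plan was calculated for another test. A result between the two thresholds would be open to dispute, and a choice of threshold made after seeing the data could look driven by the result.

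**Working it through.** **Inputs (all from Section 16.1, except the one-sided level, which is from Section 16.21).** p₁ = 0.18 (5 mg), p₂ = 0.09 (2.5 mg), difference 0.09, n = 176 per arm. Critical values: 1.960 (two-sided 5%) and 1.645 (one-sided 5%).

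**Standard errors.**
- Under the alternative: SE₁ = √[(0.18×0.82 + 0.09×0.91)/176] = √(0.2295/176) = 0.03611.
- Under the null, at the average rate 0.135: SE₀ = √(2×0.135×0.865/176) = 0.03643.

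**Step 1: reproduce the plan's figure (two-sided 5%).**
- Pooled: Φ[(0.09 − 1.960×0.03643)/0.03611] = Φ(0.515) = 69.7%.
- Unpooled: Φ(0.09/0.03611 − 1.960) = Φ(0.532) = 70.3%.
- Exact binomial enumeration of the pooled Z test: 70.6%.

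The stated 70% is right for the two-sided test.

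**Step 2: the test in Section 16.21 (one-sided 5%).**
- Pooled: Φ[(0.09 − 1.645×0.03643)/0.03611] = Φ(0.833) = 79.8%.
- Unpooled: Φ(2.492 − 1.645) = Φ(0.847) = 80.2%.
- Exact: 80.2%.

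The stated 70% does not describe this test.

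**Step 3: side by side.**

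| | Two-sided 5% (16.1) | One-sided 5% (16.21) |
|---|---|---|
| Power, 176 per arm (pooled) | 69.7% | 79.8% |
| Power, 185 per arm (pooled) | 71.8% | 81.5% |
| Nominal error in the claimed direction | 2.5% | 5% |
| Exact error, 176 per arm, both arms at 9%, 13.5% or 18% | 2.47–2.53% | 4.93–5.11% |
| Smallest significant observed difference, z×SE₀ | 1.960×3.643 = 7.1 points | 1.645×3.643 = 6.0 points |

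The 185-per-arm row is an upper bound. That number includes the allowance for ineligible and cancelled patients, and the primary analysis needs at least one dose.

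**Step 4: how often the choice matters.** With the exact figures, the chance of landing between the thresholds is 80.2% − 70.6% = 9.6% under the design alternative. At a common rate of 13.5% it is 4.9% − 2.5% = 2.4%.

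An example is 18/176 events on 2.5 mg and 30/176 on 5 mg. The difference is 12/176 = 0.0682 and the pooled rate is 48/352 = 0.1364, so SE₀ = 0.0366 and Z = 1.86. The one-sided p is 0.031 and the two-sided p is 0.062. This is significant under Section 16.21 but not under the test in Section 16.1.

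**Step 5: does the sample size show which test was intended?** With the unpooled formula, n per arm = (z_α + z_β)² × 0.2295/0.09².
- 70% power, two-sided 5%: (1.960 + 0.524)² × 28.33 = 174.9.
- 80% power, one-sided 5%: (1.645 + 0.842)² × 28.33 = 175.2.

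The pooled formula gives 178 for both. The sums 2.484 and 2.486 nearly coincide whatever the event rates, so 176 fits either reading and cannot settle the question.

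**The case against.** The best reply is that the operative test is clear. Only Section 16.21 defines the primary analysis. One-sided 5% is stated three times and fits the directional hypothesis, while the two-sided wording is a parenthesis in a sizing paragraph that sets no success rule. On that reading the plan has one decision rule and a mislabelled power statement. The error is also on the safe side: the specified test has about 80% power, more than claimed. A pre-specified one-sided 5% test is not in itself a mistake.

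Much of this stands. An analyst would follow Section 16.21, the trial is not too small for that test, and the fit of 176 to both tests is general arithmetic, not evidence of a second design. It does not remove the contradiction, because Section 16.21 itself says the study is powered for its analysis and so invokes the calculation in Section 16.1. The higher power is also not free: it comes from doubling the directional error, and the plan gives no reason for accepting that.

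**Conclusion.** The concern holds and must be fixed. The plan states two incompatible specifications for its only primary test. At 9% versus 18% and 176 per arm, power is about 70% under one and 80% under the other, and the error in the claimed direction is 2.5% or 5%. The threshold moves by about 1.1 percentage points of observed difference (7.1 versus 6.0), and the outcome depends on the rule in about 10% of trials if the design assumptions are true. These figures rest on the plan's own event rates, 176 analysed patients per arm and a Z test without continuity correction. The contradiction itself rests on wording alone and does not depend on them.

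**What to change.** State one level and one sidedness, and use it in every place. There are two coherent versions:

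1. **Align the analysis to the sizing.** Make Section 16.21, including its sentence covering all tests, and Section 16.22 two-sided 5% (or one-sided 2.5%). The 70% power and 352/370 patients then stand. The cost is the stricter threshold, with the power the plan already states. Reaching 80% power under this version would need 226 per arm (452 in total, pooled formula), but that is not required to remove the contradiction.
2. **Align the sizing to the analysis.** Correct Section 16.1 to one-sided 5% (equivalent to two-sided 10%) with about 80% power at 176 per arm, and give the reason for accepting 5% error in the claimed direction. This is the smaller edit.

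The first is preferable because it keeps the published sample-size statement true and the directional error at the level used for sizing. Either removes the contradiction. Section 16.23 borrows its method from Section 16.21, so its sidedness should be stated too. The change costs wording only, with no extra patients. It should be made before treatment codes are opened for analysis; the documents do not show what stage the trial has reached.

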8.0 Dosage Modification Based on Adverse Events

8.1 Apixaban is cleared through several mechanisms including renal clearance, hepatic metabolism, and fecal excretion. Severe thrombocytopenia, liver and renal failure may increase bleeding risk. Patients with calculated creatinine clearance ≤ 30 ml/min (using the Cockcroft-Gault formula) must hold treatment until renal function improves to creatinine clearance >30 ml/min. They may get alternative anticoagulation treatment during this time period until renal function improves per the attending physician judgment.

For patients receiving either a strong CYP3A4 inducer or a strong CYP3A4 inhibitor (Appendix II), the medication should be discontinued or an alternative agent within the specific class of drug should be sought in order to participate in this study. If no good alternative agent within that class can be identified and the drug is required, the ACCRU Data Manager should be notified and the subject removed from the trial and go to observation.

For thrombocytopenia ($> 50,000/\text{microliter}$), no dose adjustment is necessary. For thrombocytopenia ($< 50,000/\text{microliter}$), apixaban will be held until platelet count recovers. Once the platelet count improves ($\geq 50,000/\text{microliter}$), the apixaban dose should be restarted.

If patients meet criteria for a major bleed, they will have met a major safety endpoint and will be removed from the study. The patient will then be managed, off-study, as appropriate per the clinical situation and current guidelines.

If patients meet criteria for a recurrent venous thromboembolic event, they will have met a major secondary endpoint and will be removed from the study. The patient will then be managed, off-study, as appropriate per the clinical situation and current guidelines.

If the patient suffers a non-major clinically relevant bleeding event, they will have met a major safety endpoint. Medical management will be provided in accordance with the location and severity of the bleeding event. This may include temporary cessation of study medication. Once the bleeding event has been appropriately managed, they can restart study medication, if considered clinically appropriate by the attending physician, and can be followed appropriately per protocol. They do not need to be removed from the study for this event.

8.2 Patients requiring any invasive procedure requiring temporary anticoagulant cessation will be managed as follows:

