11.0 Treatment Evaluation Using RECIST Guideline – Not applicable

12.0 Descriptive Factors – Not applicable

13.0 Treatment/Follow-up Decision at Evaluation of Patient

13.1 A patient is deemed *ineligible* if after registration, it is determined that at the time of registration, the patient did not satisfy each and every eligibility criteria for study entry. The patient may continue treatment off-protocol at the discretion of the physician as long as there are no safety concerns, and the patient was properly registered. The patient will go off study.

- If the patient received treatment, all data up until the point of confirmation of ineligibility must be submitted.
- If the patient never received treatment, on-study material must be submitted.

13.2 It is deemed a *major violation*, if protocol requirements regarding treatment of the patient in cycle 1 of the initial therapy are severely violated that evaluability for primary end

point is questionable. This determination needs to be made by an investigator blinded to treatment allocation.

- 13.3 It is deemed a *cancel* if the patient is removed from the study for any reason before any study treatment is given. On-Study material and the End of Active Treatment/Cancel Notification Form must be submitted. No further data submission is necessary
- 13.4 If the patient meets criteria for a major bleed, they will have met a major safety endpoint and will be removed from the study. All data up until the point of major bleed should be entered. The patient will then be managed as appropriate per the clinical situation and current guidelines.
- 13.5 If the patient meets criteria for a recurrent venous thromboembolic event, they will have met a major secondary endpoint and will be removed from the study. All data up until the point of a recurrent venous thromboembolic event should be entered. The patient will then be managed as appropriate per the clinical situation and current guidelines.
- 13.6 If the patient suffers a non-major clinically relevant bleeding event, they will have met a major safety endpoint. Medical management will be provided in accordance with the location and severity of the bleeding event. This may include temporary cessation of study medication. Once the bleeding event has been appropriately managed, they will restart study medication and will be followed appropriately per protocol. They will not be removed from the study for this event.

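### The only event time in 16.21 stops at the first bleed of either type, so the separate major-bleed cumulative incidence omits major bleeds that follow a non-major bleed

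*Combined protocol and SAP*

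**What the plan says.** Section 16.21 sets the primary analysis as a comparison of "the proportion of patients experiencing at least one bleeding event within 12 months of beginning treatment". It then lists further analyses of that endpoint, which it labels as additional and secondary:

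- A frequency table: "frequency of major bleeding and clinically relevant non-major bleeding will be tabulated by treatment arm". No first-event limit is attached.
- Cumulative incidence functions. The competing risks are death without either type of bleed, together "with adverse events that results in termination of treatment (including vascular events) as competing risks".
- One event time for these functions: from randomization to "the first occurrence of a major bleeding, a clinically relevant non-major bleeding, death without major bleeding or clinically relevant non-major bleeding", or a treatment-ending adverse event.
- Reporting: curves are plotted for both bleed types, and incidence "will be summarized as a combined endpoint and separate endpoints by treatment arm". The difference between arms at 6 and 12 months is tested for the combined endpoint.

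Follow-up differs by type of bleed. After a CRNM bleed, section 8.1 says "They do not need to be removed from the study for this event" and section 13.6 says "They will not be removed from the study for this event". The two sections differ on whether restarting study drug is left to the attending physician, and should be reconciled, but both keep the patient on study. After a major bleed, section 13.4 says "If the patient meets criteria for a major bleed, they will have met a major safety endpoint and will be removed from the study".

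**The concern.** A time that ends at the first of either bleed suits the composite. It does not suit a separate major-bleed curve. A patient whose clock stopped at a CRNM bleed can no longer contribute a major bleed, although that patient is still followed and still assessed every 30 days. Because a major bleed ends study participation, the omission falls on major bleeds.

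The CRNM threshold is low: section 2.11 counts overt bleeding that leads only to an unscheduled contact with the care team. Such an event would keep a later intracranial bleed out of the curve.

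Major bleeding is the gravest component of the endpoint. Its incidence would be understated, and by more in the arm with more CRNM bleeding, which under the trial's own hypothesis is the 5 mg arm. The intent-to-treat safety analysis in 16.22 uses the same approach and would inherit the problem. One report could also show a major-bleed count in the frequency table that disagrees with the curve.

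**Working it through.** **Plan's own figures.** Section 16.1 adds 3.2% and 14.5% to get 17.7%, and plans on 18% against 9% with 176 per arm, two-sided 5%. The mean proportion is 0.135.

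- Null standard error: √(2 × 0.135 × 0.865 / 176) = 0.03643.
- Alternative standard error: √((0.09 × 0.91 + 0.18 × 0.82) / 176) = 0.03611.
- Power: Φ[(0.09 − 1.96 × 0.03643) / 0.03611] = Φ(0.515) = 69.7%.

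This agrees with the stated 70%. Neither that calculation nor the binary primary endpoint uses the event time in question.

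**Inputs for the check.**

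- 5 mg arm: 12-month rates of 3.2% major and 14.5% CRNM, as cited in 16.1.
- 2.5 mg arm: half of each, 1.6% and 7.25%. This is an assumption; the plan halves only the composite.
- k: the factor by which the major-bleed hazard changes after a CRNM bleed. This is an assumption, as the documents give no value.
- Constant hazards, and no deaths in the base case.

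**Formulas.** Time is in years. λM = −ln(1 − major rate), λC = −ln(1 − CRNM rate), s = λM + λC.

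- Major bleed as first bleed, which the definition counts: F = (λM / s)(1 − e^(−s)).
- First major bleed after a CRNM bleed, which it omits: A = λC × [(1 − e^(−s))/s − (e^(−kλM) − e^(−s))/(s − kλM)].
- Share omitted: A / (F + A).

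**5 mg arm.** λM = 0.03252, λC = 0.15665, s = 0.18918, e^(−s) = 0.968 × 0.855 = 0.82764.

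- F = (0.03252 / 0.18918) × 0.17236 = 0.0296.
- k = 1: F + A = 0.0320, so A = 0.0024. The share is 7.4%, and 176 × A = 0.42 events.
- k = 3: A = 0.15665 × [0.91110 − (0.90704 − 0.82764)/(0.18918 − 0.09757)] = 0.0070, a share of 19.0%.

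**2.5 mg arm.** λM = 0.01613, λC = 0.07526, e^(−s) = 0.984 × 0.9275 = 0.91266.

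- F = (0.01613 / 0.09139) × 0.08734 = 0.0154.
- k = 1: A = 0.0160 − 0.0154 = 0.0006, a share of 3.7%.

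**Results, no deaths.** The hazard before a CRNM bleed is held fixed, so total major-bleed incidence rises with k.

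| k | 5 mg: counted / all | Omitted | Events per 176 | 2.5 mg: counted / all | Omitted | Events per 176 | RR counted / all |
|---|---|---|---|---|---|---|---|
| 1 | 2.96% / 3.20% | 7.4% | 0.42 | 1.54% / 1.60% | 3.7% | 0.10 | 0.52 / 0.50 |
| 3 | 2.96% / 3.66% | 19.0% | 1.22 | 1.54% / 1.72% | 10.1% | 0.31 | 0.52 / 0.47 |
| 5 | 2.96% / 4.10% | 27.7% | 2.00 | 1.54% / 1.83% | 15.7% | 0.50 | 0.52 / 0.45 |

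RR is 2.5 mg over 5 mg.

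**Sensitivity.**

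- With 40% assumed 12-month mortality, the omitted shares for k = 1 to 5 are 6.8-25.9% (5 mg) and 3.4-14.5% (2.5 mg).
- If k is below 1, the loss is smaller than in the first row; at k = 0 it is nil.
- If both arms had the same 3.2% major-bleed rate and k = 1, the definition would give an RR of 0.0308 / 0.0296 = 1.04 instead of 1.00. Movement toward 1 therefore depends on the 2.5 mg arm truly having fewer major bleeds.

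**The case against.** The strongest reply is that the definition was meant for the composite only. It sits among analyses of the primary endpoint, and both its wording and its competing death event fit that endpoint. No sentence says that an earlier CRNM bleed ends risk for the major-bleed curve. A reader might infer an explicit rule that excludes these bleeds; the text does not go that far. It gives one definition, reports separate endpoints in the same paragraph, and supplies no other event time. The composite-only reading does not repair this. The listed competing death is one without either type of bleed, so in a separate major-bleed analysis a death after a CRNM bleed would be neither an event nor a competing event. The text needs changing on either reading.

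A reader might also infer that later major bleeds vanish from the report. The documents do not support that. Bleeding is graded on a form at each monthly evaluation (section 18.1), and the frequency table in 16.21 has no first-event limit.

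The scale is small, and this stands. At 3.2%, 176 × 0.032 = 5.6 major bleeds are expected in the 5 mg arm. The standard error of that rate is √(0.032 × 0.968 / 176) = 1.3 percentage points, against an omission of 0.2 to 1.1 points. The multipliers of 3 and 5 have no source in the documents. A lower hazard is also plausible: section 8.1 allows study drug to be stopped temporarily, and 16.21 focuses on events during treatment or within 7 days of stopping.

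Finally, curves split by type of first bleed are a coherent choice, because they add up to the composite. That is true, but they then estimate the incidence of major bleeding as the first bleed, which the plan does not say and a reader would not assume.

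**Conclusion.** The point holds for the cumulative-incidence analyses of 16.21 and the analyses that reuse their approach. Applied as written, the separate major-bleed curve and estimate omit first major bleeds that follow a CRNM bleed. The omission is about 7% (5 mg) and 4% (2.5 mg) with independent hazards, and about 19-28% and 10-16% if the later hazard is three to five times higher. In events, it is roughly 0.4-2.0 and 0.1-0.5 per 176 patients. The risk ratio reads 0.52 instead of 0.50-0.45.

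These sizes rest on the cited component rates applying to the 5 mg arm, on halving both in the 2.5 mg arm, on constant hazards and on assumed multipliers.

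A reader might go further and conclude that the trial's main result is biased. It is not: the primary test is a binary composite, its power is unaffected, and the planned 6- and 12-month difference test on the incidences is for the combined endpoint. This is a definition worth correcting in secondary analyses of the most serious outcome.

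**What to change.** In 16.21, keep the present event time for the composite and add one definition for each component:

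- **Major bleeding:** time to first major bleed, regardless of any earlier CRNM bleed. Competing events are death without a major bleed, whether or not a CRNM bleed came first, and, if kept, treatment-ending adverse events other than the major bleed itself.
- **CRNM bleeding:** time to first CRNM bleed. Competing events are a major bleed (because it ends study follow-up), death without a CRNM bleed and, if kept, treatment-ending adverse events.

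State that 16.22 and the Cox sensitivity analysis follow the same definitions wherever they address a component. No new data are needed, and the cost is a few sentences. The one downside is that a patient can appear in both component curves, which will then no longer sum to the composite; a footnote should say so. If curves that sum are also wanted, label them as type of first bleed.

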No formal interim analysis is planned. Risk-benefit will be evaluated by the Mayo Clinic Data Safety and Monitoring Board (DSMB), which will give regular recommendation to the executive committee. Early termination of accrual will be considered if there is evidence of a significant difference in major bleeding rates between the comparators. Access to interim tabular risk benefit data will be restricted.

16.5 Adverse Event Stopping Rule:

The stopping rule specified below is based on the knowledge available at study development. We do note that the Adverse Event Stopping Rule may be adjusted in the event of either (1) the study re-opening to accrual or (2) at any time during the conduct of the trial and in consideration of newly acquired information regarding the adverse event profile of the treatment(s) under investigation. The study team may choose to suspend accrual because of unexpected adverse event profiles that have not crossed the specified rule below.

Accrual will be temporarily suspended to this study if at any time we observe events that the study team considers to be at least possibly related to study treatment (i.e., an adverse event with attribute specified as “possible,” “probable,” or “definite”) that satisfy the following:

- If 5 or more patients in the first 20 treated patients of either of the study arms (or 20% of all patients after 20 are accrued) experience a grade 4 or higher non-hematologic adverse event.

We note that we will review grade 4 and 5 adverse events deemed “unrelated” or “unlikely to be related” to verify their attribution and to monitor the emergence of a previously unrecognized treatment-related adverse event.

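### Section 16.5: after the first 20 patients the accrual-suspension rule no longer names an arm and, read literally, pools the two doses, which weakens detection of an excess in one arm

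*Combined protocol and SAP*

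**What the plan says.** Section 16.5 is a continuous rule: "Accrual will be temporarily suspended to this study if at any time we observe events" that are at least possibly related to treatment and meet the criterion that follows. The criterion has two limbs. The first names its denominator: "If 5 or more patients in the first 20 treated patients of either of the study arms". The second follows in parentheses: "or 20% of all patients after 20 are accrued". Both count patients who "experience a grade 4 or higher non-hematologic adverse event".

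Two other provisions bear on the point. Section 16.5 leaves room for judgement: "The study team may choose to suspend accrual because of unexpected adverse event profiles that have not crossed the specified rule below". Section 16.4 plans no formal interim analysis but says: "Early termination of accrual will be considered if there is evidence of a significant difference in major bleeding rates between the comparators". Section 16.1 sets the allocation ("Patients will be randomized at a 1:1 ratio to receive either 5 mg or 2.5 mg of apixaban twice daily") and a total of 370 patients, 185 per arm.

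The documents give no expected rate for the event that the rule counts and no operating characteristics for the rule.

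**The concern.** Between the two limbs the denominator changes in three ways. The reference to an arm disappears, treated patients become accrued patients, and it is not stated whether the second 20 is per arm or in total. Taken at its word, the second limb pools the two doses.

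The trial is built on the hypothesis that the doses differ in safety, so an excess in one arm is the pattern a monitoring rule should be able to see. Pooling averages that excess with the quieter arm. The first limb concerns at most 20 patients per arm, 40 of 370. For the other 330 the only numerical limit is the second limb. At stake is how reliably accrual would pause for a harmful excess confined to one dose, above all among patients enrolled after each arm's first 20.

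**Working it through.** **Inputs.** From Section 16.5: 5 of 20 per arm, then 20%, checked at any time. From Section 16.1: 1:1 allocation, 185 per arm. The true event rates are assumptions, because the plan gives none. There is no stated figure for this rule to reproduce, and the power figure in Section 16.1 does not bear on it.

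**Step 1: what the pooled limb responds to.** With equal arms the expected pooled proportion is (pA + pB)/2. It reaches 20% when pA + pB = 40%. If one arm is at 5%, the other must be at 35%.

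**Step 2: first limb, one arm.** P(X ≥ 5) with X ~ Binomial(20, p) is 0.3% at p = 5%, 37% at 20%, 59% at 25%, 76% at 30%, 88% at 35% and 95% at 40%.

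**Step 3: second limb at a single look.** With n per arm, the pooled limit is P(XA + XB ≥ 0.20 × 2n): 16 of 80, 40 of 200 and 74 of 370 at n = 40, 100 and 185. The per-arm limit, for the high arm alone, is P(XA ≥ 0.20n): 8 of 40, 20 of 100 and 37 of 185. Exact binomial calculation gives:

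| True rates | Pooled, n = 40 / 100 / 185 | High arm alone, n = 40 / 100 / 185 |
|---|---|---|
| 25% vs 5% | 13% / 3% / 0.4% | 82% / 90% / 95% |
| 30% vs 5% | 31% / 19% / 10% | 94% / 99% / >99.9% |
| 30% vs 10% | 55% / 53% / 52% | 94% / 99% / >99.9% |
| 40% vs 5% | 77% / 85% / 91% | >99% at each |

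When the average is below 20%, the pooled limb becomes less likely to cross as patients accumulate, while the per-arm limit becomes more likely to cross.

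**Step 4: the whole rule, continuous looks.** Simulation of 20,000 trials, 185 per arm, a look after each pair of patients, outcomes known at once, and the second limb starting at 21 per arm:

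| True rates | Literal rule (second limb pooled) | Both limbs per arm |
|---|---|---|
| 20% vs 5% | 38% | 87% |
| 25% vs 5% | 62% | 99% |
| 30% vs 5% | 82% | 100% |
| 5% vs 5% | 0.5% | 1.5% |
| 10% vs 10% | 10% | 25% |

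If the pooled limb instead starts soon after 20 patients in total, the literal rule gives about 41%, 64% and 83% in the first three rows, so this ambiguity matters less than the missing arm.

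**Step 5: an excess that begins after an arm's first 20 patients.** One arm runs at 5% in its first 20 patients and 25% afterwards, the other at 5% throughout. The literal rule triggers in about 2% of trials and the per-arm rule in about 92%. With 30% afterwards the figures are about 10% and over 99%. Here the first limb has nothing to detect, so the result rests on the second limb.

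**The case against.** A reader might infer that once 20 patients are in, a large one-arm excess will usually go undetected and patients will keep being randomised to the worse arm for the remaining 330 places. The documents do not support that.

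- The first limb is per arm and does not expire. Monitoring is at any time and treatment lasts 12 months, so later events in each arm's first 20 patients still count. Restricted to trials in which the first limb did not cross, the second limb triggers in about 8% pooled against 98% per arm at 25% vs 5%, and about 24% against 100% at 30% vs 5%. Those figures leave out the trials already caught. The whole literal rule triggers in 62% and 82%.
- Where the two rates average 20% or more, the pooled limb triggers more often than not. Among trials not caught by the first limb, it does so in about 59% at 35% vs 5% and about 91% at 40% vs 5%.
- The wording is ambiguous. The parenthesis follows directly on the reference to either arm, and the phrase about all patients could be meant only as a contrast with the first 20. Pooled is the more literal reading, but the text does not settle it.
- The DSMB reviews risk and benefit and may act on a difference in major bleeding, and the study team may suspend accrual without a crossing.
- The illustrative rates are high. Section 16.1 cites 3.2% major bleeding in cancer patients on direct inhibitors. At 6% vs 3% the rule triggers in about 0.6% of trials as written and about 2% per arm, so neither version would detect a modest dose difference.

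All of this stands, and it limits the size of the point. It does not remove it. The safeguards outside the rule carry no numerical boundary, the DSMB criterion concerns major bleeding only, and the trial is double-blind with restricted access to interim data, so a team without arm-level data may not see a one-arm excess.

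**Conclusion.** The point holds as a cheap improvement. The second limb should name its denominator because, read literally, it pools the doses and is insensitive to a one-arm excess unless the two rates sum to about 40%. For an excess present from the start, the literal rule gives up roughly 18 to 49 percentage points of detection: 38% against 87%, 62% against 99% and 82% against 100%. For an excess that starts after an arm's first 20 patients it gives up nearly all of it (2% against 92% at 25%). It would be wrong to say that the rule as a whole usually fails, or that accrual would not be suspended.

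The figures rest on assumed event rates, 185 per arm, continuous looks and outcomes known at once. Reporting delay would lower early crossing under either reading.

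**What to change.** Keep the plan's own thresholds and reword the second limb in Section 16.5 so that 20% applies to the treated patients of either arm, once more than 20 have been treated in that arm. State that the DSMB or an unblinded statistician applies the rule by arm, since the study team is blinded. Add a short table of the rule's operating characteristics under a few assumed rates. If pooling was intended, say so and give the reason.

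The edit is one or two sentences plus the table, and Section 16.5 already allows the rule to be adjusted during the trial. The price is more temporary pauses when the arms do not differ: about 25% of trials against 10% with both arms at 10%, and about 1.5% against 0.5% with both at 5%. A crossing suspends accrual temporarily and does not end the trial.
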